1.1. Administrative information

1.1.1. Trial registration

This study has been prospectively registered on the Australia New Zealand Clinical Trials Registry (ANZCTR) http://www.anzctr.org.au/ (ACTRN12618000705280).

1.1.2. Sponsor

This is an investigator-initiated study, sponsored by The University of Melbourne.

1.1.3. Funding

This study will be funded by the [name] research laboratory funds from the Department of Optometry and Vision Science, The University of Melbourne. Support for the project includes a Melbourne Neuroscience Interdisciplinary grant and a Rebecca L Cooper Medical Foundation research grant.

1.1.4. Expected duration of study

This study is expected to run for a total of 2.5 years from recruitment to the completion of the last participant's last visit. The length of treatment for an individual participant, including all follow-up visits, is six months.

1.2. Background and rationale

Diabetic neuropathy is the most common complication of diabetes mellitus, affecting >50% of individuals with the condition (Dyck & Dyck, 1999). The Diabetes Control and Complications Trial demonstrated that intensive blood glucose control could reduce the incidence of neuropathy and potentially slow progressive nerve damage (Albers *et al.*, 2010; Nathan *et al.*, 1993); however, there are currently no clinical therapies for attenuating the onset or progression of neuropathy.

Omega-3 polyunsaturated fatty acids (PUFAs) are essential fatty acids that cannot be synthesised by the human body. Increased consumption of omega-3 PUFAs endogenously generates anti-inflammatory and pre-resolving mediators that have been shown to be beneficial in a range of inflammatory conditions (Simopoulos, 2002). Once ingested, omega-3 PUFAs are incorporated into cell membranes, and play a role in cellular signalling and gene expression (Calder & Grimble, 2002), and maintaining nerve integrity. In animal models of diabetes, omega-3 supplementation can attenuate adverse changes in nerve structure and function (Gerbi *et al.*, 1999; Yee *et al.*, 2010). Derivatives of omega-3 fatty acids have also been shown to restore corneal nerve integrity and restore damage after corneal injury in rabbits (Cortina *et al.*, 2010). However, there has been limited investigation in humans, particularly as related to diabetic neuropathy.

There is some clinical evidence to suggest that omega-3 oral supplements may be useful in treating peripheral neuropathy in diseases other than diabetes. For example, omega-3 supplementation was shown to reduce the severity of symptoms and improve total neuropathy score in paclitaxel-induced peripheral neuropathy (Ghoreishi *et al.*, 2012). Our laboratory has recently shown that omega-3 fatty acids promote corneal nerve regeneration in dry eye disease, which is characterised by a mild degree of corneal neuropathy (Chinnery *et al.*, 2017a). Furthermore, a recent open-label, proof of concept study involving a single-arm of participants with type-1 diabetes, treated for 12 months with omega-3 PUFAs, reported a 20% increase in small nerve fibres using corneal nerves as a primary outcome measure (Lewis *et al.*, 2017). Together, these promising findings provide the rationale for the present proposal, being a randomised, double-masked, placebo-controlled clinical trial to assess the effects of a six-month period of supplementation with omega-3 PUFAs on small nerve fibre structure and function, measured both in the eye and the extremities of the body, in individuals with type-1 diabetes.

JUSTIFICATION OF ASSESSMENT APPROACHES: Ocular manifestations of diabetes in the anterior eye include changes in tear film integrity, impaired wound healing and diabetic cataract, and in the posterior eye, diabetic retinopathy (Negi & Vernon, 2003). Studies suggest that there is an association between peripheral neuropathy and ocular surface complications in diabetes, especially in relation to reduced corneal nerve density and sensitivity, where both reductions in corneal nerve structure and function have been shown to correlate with the severity of diabetic peripheral neuropathy (Malik *et al.*, 2003; Pritchard *et al.*, 2010). Damage to small nerve fibres, including unmyelinated C-fibres and thinly myelinated A δ -fibres, is recognised to precede the involvement of larger nerve fibres (Breiner *et al.*, 2014; Greene *et al.*, 1999).

Corneal *in vivo* confocal microscopy (IVCM) is the only technique that allows non-invasive imaging of the peripheral nerves in the body. It has been proposed to detect the earliest stages of change that precede the development of large fibre neuropathy in diabetes (Pritchard *et al.*, 2015), and to serve as a marker to monitor changes in neuropathy (Tavakoli *et al.*, 2013). In this study, the structure of the corneal nerves will be visualised using IVCM; we will quantify changes in corneal nerve parameters, as a primary efficacy outcome measure, between baseline and the primary endpoint (six months).

Other ocular parameters to be examined include: tear film integrity, examined using standard clinical techniques (e.g., tear osmolarity, ocular surface staining, inflammatory tear markers) and corneal nerve function (i.e., using corneal aesthesiometry). Routine dilated fundus examination will be performed, being a standard clinical procedure in individuals with diabetes, to assess for any changes of retinal health throughout the study.

In addition to the eye health investigations, we will assess whether there are changes to small nerve fibre function in the peripheral body (ie., feet) using electrophysiology testing methods (i.e., cutaneous silent periods, which assesses thinly myelinated A δ -fibres) and autonomic testing (i.e., quantitative sudomotor axonal reflex testing, which assesses unmyelinated post-ganglionic sudomotor C-fibres) and quantitative sensory testing, to assess thermal (cold: A δ -fibres and warm: C-fibres) and vibration (medium myelinated fibres: A β) thresholds. Routine nerve conduction studies will also be performed to assess any large nerve fibre damage, and nerve excitability testing, using similar techniques, will detect any changes in these nerve fibres that may precede large nerve fibre damage.

JUSTIFICATION OF COMPARATOR:

Olive oil is chosen as the comparator for omega-3 interventions, as an inert control. The main constituents of olive oil are omega-9 oleic acid (C18:1), which has shown to have no effect in the inflammatory mediators in the body. Olive oils also matches in caloric intake of the active oral supplementation. Participants of double-masked clinical trials have demonstrated a poor ability to differentiate between active fish oil and inactive olive oil as their given intervention, even if they notice a fishy aftertaste (Damico *et al.*, 2002).

2. Study design and participants

2.1. Study objectives

2.1.1. Primary objective

The aim of this randomised, double-masked, placebo-controlled clinical trial is to evaluate the effects of a six month supplementation period with omega-3 polyunsaturated fatty acid (PUFA) supplements on peripheral nerves in individuals with type-1 diabetes.

2.2. Study design

This study is a single-centre, double-masked, randomised, two-arm, parallel-group interventional study comparing the effects of omega-3 EFA oral supplements with olive oil (placebo) supplements over six months. Participants will be randomised according to a 1:1 allocation ratio to omega-3 PUFA supplements (defined below) or an olive oil (placebo) supplement.

The primary outcome measure is the change in central corneal nerve fibre length (CNFL) from baseline (Day 1); the primary analysis endpoint is Day 180 (six months).

2.3. Study setting

This study will be conducted at the Department of Optometry and Vision Sciences at The University of Melbourne, with recruitment and data collection undertaken both at this site and the Endocrinology and Neurology Departments at St Vincent's Hospital, Melbourne.

2.4. Study population and entry criteria

2.4.1. Number of participants

A total of 50 patients will be randomised over the study duration.

Given a two-arm parallel design, with the pre-specified primary outcome of CNFL (taken as a continuous measure), for 80% power at a confidence level of 95%, using an estimated true difference between intervention arms of 2.9 units, mm/mm² (Chinnery *et al.*, 2017b), based on an expected standard deviation of 3.2 units, the required sample size is 21 participants per group. To allow for 15% participant attrition, the sample size within each group will be increased by this amount, giving a need to recruit a total of 25 participants in each interventions arm (n=50 for the trial).

2.4.2. Study population characteristics

Participants will be individuals with type-1 diabetes mellitus, for any length of duration, with or without diagnosed neuropathy.

2.4.3. Inclusion criteria

The following are requirements for entry into the study at Visit 1 (Baseline):

- 1. Male or female, ≥ 18 years of age
- 2. MNSI >2
- 3. Written informed consent and documentation, in accordance with privacy requirements, obtained prior to performing any study procedures;
- 4. Distance best-corrected visual acuity of at least 6/12 Snellen equivalent in **each** eye using a standard visual acuity chart;
- 5. Intraocular pressure (IOP) \leq 21 mm Hg in both eyes;

[Note: Participants with primary open-angle glaucoma or ocular hypertension (OHT) may be eligible to participate, provided they are on **stable** monotherapy **bilaterally**, with both eyes IOPs controlled and under 21 mmHg at the baseline visit. Any topical IOP-lowering medications must have a start date of \geq 3 months prior to Visit 1, with the dosage not expected to change during the study.]

6. Ability to understand and follow study instructions, with the intention of completing all required study visits.

2.4.4. Exclusion criteria

The following are criteria for exclusion from participating in the study at Visit 1 (Baseline):

Systemic

- 1. Any uncontrolled systemic disease, other than sub-optimally controlled diabetes mellitus:
- 2. Confirmed neuropathy secondary to causes other than diabetes (e.g., alcohol polyneuropathy. Vitamin B-12 deficiency, folate deficiency, chronic renal failure, hypothyroidism, neurotoxic drug use including chemotherapy);
- 3. Any of the following general medical conditions: bipolar disorder, atrial fibrillation, implanted defibrillator, familial adenomatous polyposis, systemic immunocompromise;
- 4. Scheduled or planned systemic surgery over the course of the study;
- 5. Any known bleeding disorders;
- 6. Current consumption of a systemic anti-coagulant medication other than aspirin;
- 7. Females who are currently pregnant or breastfeeding;
- 8. females of childbearing potential who are planning a pregnancy over the course of the study;

[Definition: For the purposes of this study, females will be considered of childbearing potential unless they are: naturally postmenopausal or permanently sterilised (i.e., a **full** [not partial] hysterectomy). Natural menopause is defined as the permanent cessation of menstrual periods, determined retrospectively after a woman has experienced 12 months of amenorrhea without any other obvious pathological or physiological cause.

If a female participant does become pregnant over the course of the study, the participant will be asked to attend for a 'Study Exit' final visit, and will then be exited from the study with appropriate follow-up **under the direction of the principal investigator**. The **principal investigator** will notify the patient's GP that the patient was being treated with an oral supplement; if necessary, the mask can be broken.]

9. Inability to sit/lie supine comfortably during the examination procedures for any reason.

Ophthalmic

- 10. Known allergy to or previous reaction to any ocular agents used in the study (i.e., ocular anaesthetics, sodium fluorescein, lissamine green, ocular mydriatics);
- 11. Scheduled or planned ocular surgery or procedure over the course of the study;
- 12. Any history of rigid contact lens wear;
- 13. Grading of diabetic retinopathy worse than moderate retinopathy according to the simplified ETDRS (Wisconsin) classification (ETDRS Research Group, 1991);
- 14. Presence of any of the following ocular conditions: active ocular infection or inflammation that in the judgment of the investigator may interfere with the interpretation of the study results;
- 15. Corneal abnormalities or damage that could disrupt normal corneal nerve morphology, including keratoconus, bullous keratopathy, advanced corneal dystrophies, history of neurotrophic keratopathy including herpes keratitis, severe Sjogren's associated dry eye disease:
- 16. History of refractive surgery or trauma within the past 12 months;
- 17. Use of autologous serum eye drops within the past three months, or their anticipated use during the course of the study;
- 18. Participant has a medical or ocular condition, or is in a situation, which in the principal investigator's opinion, may put the participant at significant risk, may confound the study results, or may interfere significantly with participation in the study.

Interventional

- 19. Current or previous regular consumption of any omega-3 oral supplements (>3 times/week) in the three months preceding Visit 1;
- 20. Current participation in another interventional drug or device study or anticipated entry into such a within 1 month of enrolment;
- 21. Known allergy or hypersensitivity to any components of the study supplements;

22. Cultural or religious beliefs that exclude the consumption of certain or all animal products.

2.4.5. Recruitment methods

Initial contact with potential participants will be made in the following ways:

- i) After the treating clinician at St Vincent's Hospital or the University of Melbourne eye clinic has identified that a patient who may be eligible to participate in the study, the patient will be asked if they give verbal consent to be contacted by the investigators (either by phone/email) to receive further information. The potential participant will then also be provided with a hard copy of the PICF, and the investigator will contact the potential participant directly to discuss the study.
- ii) The co-investigator ([name]) will have information available about the study for patients who are waiting for clinical appointments at the type-1 diabetes outpatient clinic at St Vincent's Hospital. She will discuss the study with patients whilst they are waiting, and if they are interested in participating, provide them with a hard copy of the PICF and obtain permission to follow-up with them via phone and/or email.
- iii) Potential participants who have provided written consent to be contacted for research studies at the University of Melbourne eye care clinic will be identified by chart review (by one of the investigators), with a subsequent email (first preference) or mail-out (if no email details were provided) invitation. Those who respond to the invitation will be provided with the PICF, and then followed up via phone and/or email with regard to arranging a time for a baseline study visit.
- iv) Potential participants who respond to study advertisements will be contacted by one of the listed investigators, either via email or phone (depending upon the patient preference), and provided with further information (including the PICF).

3. Study Interventions and Formulations

3.1. Interventions

3.1.1. Omega-3 oral supplements

Treatment arm: triglyceride form omega-3 oral supplement (Caruso's Natural Health Triple Strength fish oil). Each 1500mg capsule contains active ingredients of 540mg Eicosapentaenoic Acid (EPA) and 360mg Docosahexaenoic Acid (DHA).

Participants will be asked to consume two capsules per day; the total active dose of omega-3 triglycerides consumed will be 1080mg EPA +720mg DHA per day for 180 days.

3.1.2. Placebo oral supplement

Control arm: Olive oil (1500mg) oral supplements, two capsules per day, manufactured by BJP Laboratories Pty Ltd, for 180 days.

3.2. Treatment regimen and dosing

Each participant will be instructed to consume two capsules each day, at any time during the day, with or without food, at least two hours before or after medication. Participants will be instructed that they may or may not notice a fishy aftertaste with either treatment options, to alter their expectations, to strengthen the double-masked.

Participants will be provided with a supplement log to document their consumption of capsules each day. Participants will be advised not to 'make up' for missed doses with additional capsules on a given day; a reason for a 'missed dose' should be documented on the supplement log, which will be returned along with any remaining capsules at Visits 3, 4 and 6.

Dose alteration is not permitted. Should participants wish to discontinue dosage for any reason, they must inform the Principal investigator immediately to withdraw from the study.

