8.1.1. Populations to be analysed

The statistical analysis will follow an intention-to-treat approach (i.e., will include data from all participants randomised into the study, regardless of whether they received the study intervention). This approach preserves the prognostic balance in the study arms achieved by randomisation.

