8.1.2. Handling of missing data

The proposed statistical approach provides valid inference in the presence of missing data if the missing data mechanism is ignorable (missing completely at random or missing at random) and includes participants who have a baseline and at least one post-baseline measurement of the primary outcome measure (CNFL). Missing values will be checked and reported across treatment arms and follow-up time points.

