10.8. Withdrawal criteria

A participant can be withdrawn from the study if he/she is not able or willing to use the study product in compliance with the protocol; a female of child-bearing potential becomes pregnant; or, if he/she is not willing to comply with the required study procedures at each visit.

Withdrawal of a participant **must** be discussed with the principal investigator, who will directly advise the participant of their need to withdraw. A 'Form of Withdrawal" must be completed by the participant indicating their intent to withdraw from the study.

11. Examination procedures, tests, equipment and techniques

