- Continuous repeated measures data collected at more than one visit will be analysed using a constrained longitudinal data analysis technique (Liang 2000). The outcome (dependent variable) will consist of the baseline and postbaseline values. The model will assume a common baseline mean across the two treatment arms due to random allocation. It will incorporate time point (study visit) as a categorical variable, thus it will not assume a specific trajectory over time. In addition to study visit, the model will include treatment as the main factor and the treatment by study visit interaction. The variancecovariance among the repeated measurements will be defined as unstructured. In the case of non-convergence, we will consider alternative structures (first-order autoregressive, Toeplitz, compound symmetry). Using this model, study participants with a missing baseline or a missing postbaseline value will be included in the analysis but study participants with no outcome values will be excluded. This model will yield unbiased results when the outcome data are Missing At Random. We will report the estimate and two-sided confidence interval of the absolute difference between two treatment groups in the change from baseline to 3 months and 6 months postbaseline (if applicable). Before fitting this model, the distribution of the outcome will be explored. In addition, we will examine if there are potential violations of underlying model assumptions (e.g. residuals). As a result, we may apply an appropriate transformation (e.g. log-transformation) before fitting the final model.
- Binary data will be analysed using a logistic regression model. We will report
 the estimate and two-sided confidence interval of the odds ratio between the
 two treatment groups.
- Categorical data will be analysed using an ordinal logistic regression model.
 We will report the estimate and two-sided confidence interval of the odds ratio between the treatment groups.

Details of which model will be used for each of the primary, key secondary, and secondary outcomes can be found in Appendix 3.

Compliance

See Table 4 in **Appendix 4**.

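### Protocol 3.2 ends follow-up when a participant stops the supplement, which undermines the intention-to-treat aim and leaves Day 180 CNFL for early stoppers to an untested missing-at-random assumption

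*Combined protocol and SAP*

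**What the plan says.** Stopping and withdrawal:

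- Protocol 3.2: "Should participants wish to discontinue dosage for any reason, they must inform the Principal investigator immediately to withdraw from the study".
- Protocol 10.8 is permissive: "A participant can be withdrawn from the study if he/she is not able or willing to use the study product in compliance with the protocol".
- Protocol 10.7 asks those who withdraw to return for an exit assessment with the content of Visit 6. By section 10.4 that includes confocal microscopy, but not the Visit 5 tests: MDNS, cutaneous silent periods, QSART, nerve conduction, excitability and bloods.
- No section describes a participant who stops the capsules but stays in outcome follow-up.

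Analysis:

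- Protocol 8.1.1 says the intention-to-treat analysis "will include data from all participants randomised into the study, regardless of whether they received the study intervention". SAP Section 3 defines it as analysis in the randomised group.
- Protocol 8.1.2 says the approach "provides valid inference in the presence of missing data if the missing data mechanism is ignorable". SAP Section 6 says of the longitudinal model: "This model will yield unbiased results when the outcome data are Missing At Random".
- SAP Sections 5 and 10 set assessments outside the visit windows to missing. The windows are Days 76 to 104 for Day 90 and Days 156 to 204 for Day 180.
- SAP Section 8 lists one sensitivity dataset, which excludes non-compliant participants.

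**The concern.** Intention-to-treat is meant to estimate the effect of being assigned to the supplement, including in people who do not keep taking it. That needs outcomes after stopping. If stopping also ends follow-up, loss of Day 180 CNFL becomes linked by design to whatever made the person stop, such as intolerance or lack of perceived benefit.

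The model then fills the gap from the participant's own earlier values and from participants in the same arm, most of whom stayed on supplement. The estimate leans towards the effect if everyone had continued, while carrying the intention-to-treat label. Missing at random is least secure for exactly these people, and the one planned sensitivity dataset drops non-compliers, which moves further from intention-to-treat.

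**Working it through.** **1. The plan's own figure.** Inputs from Protocol 2.4.1: difference 2.9, SD 3.2, two-sided 5%, 80% power, 15% attrition. The t-test calculation gives 20.12, so 21 per arm. Then 21/(1 − 0.15) = 24.7, so 25 per arm. Both stated figures reproduce. At 15%, attrition from all causes would be 0.15 × 25 = 3.75, about 4 per arm.

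**2. What happens to CNFL from an early stopper.** Combining Protocol 10.4 and 10.7 with the SAP windows:

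- Exit visit on Days 156 to 204: counts as Day 180.
- Exit visit on Days 76 to 104: counts as Day 90; Day 180 is missing.
- Any other day: not used in the analysis of either visit.

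Outcomes measured only at Visits 2 and 5 have no exit measurement, and SAP Appendix 3 analyses them at Days 1 and 180 only. A stopper who does not attend Visit 5 has no post-baseline value for them.

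**3. Missing CNFL (Table S4).**

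- Day 180: 0/21 omega-3 and 22 − 19 = 3 of 22 placebo (13.6%); 3/43 = 7.0% overall.
- Day 90: 2/21 and 4/22. All 21 omega-3 participants have a Day 180 value, so at least two missed values there were not exits.

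**4. Sensitivity of the Day 180 result.** If the three missing placebo values differ from the model's prediction by δ on average, the placebo mean, and so the effect, shifts by (3/22) × δ = 0.14 mm/mm² per 1 mm/mm².

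The complete-case difference in mean change is 2.06 − (−0.72) = 2.78. With SDs 1.73 (n = 21) and 1.68 (n = 19), the pooled SE is 0.54 and the 95% CI is 1.69 to 3.87. The reported model estimate is 2.70 (1.64 to 3.75).

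Now give all three missing placebo participants a change of v. The placebo mean becomes (19 × (−0.72) + 3v)/22:

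| v (mm/mm²) | Placebo mean | Difference | Lower 95% limit | p |
|---|---|---|---|---|
| +2.06 (omega-3 mean) | −0.34 | 2.40 | 1.30 | 0.0001 |
| +5 | 0.06 | 2.00 | 0.65 | 0.0045 |
| +8 | 0.47 | 1.59 | −0.10 | 0.064 |

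Significance is lost only when each gains about 8, against an observed placebo mean of −0.72 (SD 1.68). Holding the reported SE fixed instead, the lower limit reaches zero at δ = 1.64 × 22/3 = 12.0.

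**5. What following stoppers would cost in power.** The documents give no stopping rate or retained effect, so these are assumptions. All rows are t-based, with SD 3.2:

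- Plan's case, 21 completers per arm at 2.9: 82%.
- 25 per arm, 15% of the active arm stop and keep none of the effect: 2.9 × 0.85 = 2.465, power 76%; 80% power would need 28 per arm.
- The same, keeping half the effect: 2.9 × 0.925 = 2.68, power 83%.

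**The case against.** Four stronger readings are tempting, and the documents do not support them.

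- **That the withdrawal rule contradicts intention-to-treat.** It does not. The population is defined by randomised group, the SAP says "study participants with a missing baseline or a missing postbaseline value will be included in the analysis", and the Table S4 estimates use n = 43. The rule reduces what is collected, not who is counted.
- **That poor adherers are removed.** Protocol 3.2 has missed doses logged, 10.8 is permissive, and SAP Section 6 defines non-compliance (below 75% or above 125%) so that such participants can be excluded in a sensitivity analysis. They are therefore expected in the main dataset.
- **That a stopper has no Day 180 CNFL.** An exit visit inside the Day 180 window supplies one, and a Day 90 value, if present, also informs the model.
- **That the three missing placebo values show the damage.** The CONSORT figure is not shown, so the reasons cannot be read. The 0/21 against 3/22 split is compatible with chance (Fisher p = 0.23), and planned attrition covers all causes.

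All of this stands. It narrows the point without removing it: no document provides for follow-up after stopping, the exit visit helps only inside fixed windows, and nothing planned probes the missing-at-random assumption.

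**Conclusion.** The point holds as a weakness of design and estimand. Sections 3.2 and 10.8 need reconciling with each other and with the intention-to-treat aim of 8.1.1, and the analysis lacks a check on departures from missing at random. It should be addressed, but it does not put the reported primary result in doubt: with three Day 180 values missing, the difference stays at 2.40 or above for any assumed change up to the omega-3 mean.

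This rests on summary statistics from Table S4, on single assumed values for the three participants rather than a refit of the longitudinal model, and on no assumption about why they were lost. With heavier or more treatment-related stopping, the same rule could matter more; the documents give no rate from which to say how much.

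**What to change.** **Protocol wording.** Reconcile 3.2 and 10.8 with 8.1.1. Record stopping the study supplement separately from leaving follow-up. Invite participants who stop to attend the already scheduled Day 90 and Day 180 outcome visits, including Visit 5, and enter those data in the intention-to-treat analysis. This concerns data collection only. When or why a supplement is stopped, and the safety, eligibility and pregnancy exits in 2.4.4, 10.6, 10.7 and 10.8, are for the sponsor to reconcile.

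**Analysis.** State the estimand and say how early-exit CNFL outside the windows is used. The last visit was on 10 March 2020, so for this trial the usable part is to report who stopped the supplement and why, by arm, and to add a delta- or reference-based sensitivity analysis for Day 180 CNFL.

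**Cost.** Prospectively: a wording amendment, one or two scheduled visits for a few participants, and possibly a slightly diluted effect estimate, as shown in step 5 of the working. For the completed trial: a short table and one additional analysis.
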